### **Continuous data**

Continuous data will be summarized using number of patients (n), mean, standard deviation, median, first and third quartiles (Q1 and Q3), minimum value, and maximum value.

### **Categorical data**

Categorical data will be summarized using n and percentage.

- All categories will be presented, even if no patients are counted in a particular category, unless otherwise stated.
- A Missing category will be displayed in all tables for categories where at least one missing value exists, unless otherwise specified.
- Counts of zero in any category will be presented without percentage.
- All summary percentages will be calculated using N, unless otherwise stated in a footnote.
- For AEs, medical history, prior and concomitant medications, the counts are based on single counts of patients with multiple events/treatments under the same category, while the percentages are calculated using N. Counts will be displayed by descending order of frequency for the overall group by dictionary hierarchy.

**Precision of summary statistics**

- Integer – Sample size (n, N) and number of missing data (if displayed).
- One additional decimal place than reported/collected – Mean, median, other percentile, confidence interval.
- Two additional decimal places than reported/collected – Standard deviation.
- Same number of decimal places as reported/collected – Minimum, maximum.
- Percentages – One decimal place.

**Study day**

Study day will be calculated as (assessment date – date of first study treatment dose) for pre-baseline assessments and [(assessment date – date of first study treatment dose) + 1] for post-baseline assessments, i.e. there will be no study day 0 and study day 1 will correspond to the first study treatment dose.

**Ordering**

Data will be presented in listings in order of group, patient ID, visit, assessment date/time, and assessment type/parameters chronological order unless otherwise specified. In case of clinical laboratory results, the listings will be presented in order of group, patient ID, parameter, assessment date/time, visit.

**Date format**

Dates will be presented in format DDMMYYYY.

**Dictionaries**

Latest version of Medical Dictionary for Regulatory Activities (MedDRA) will be used for the relevant outputs.

Latest version of World Health Organization (WHO) Drug Global B3 will be used for the relevant outputs.

NCI-CTCAE v5.0 will be used for the relevant outputs.

The version will be documented in the footnote of the corresponding TFLs.

**File naming**

Each TFL output file will be named with a t, l, or f added before the TFL number to denote the output type and then according to its table numbering in the following way: Table 14.2-1.1 would be t14\_2\_1\_1, Table 14.2-11 would be t14\_2\_11, Listing 16.2.7-1.1 would be l16\_2\_7\_1\_1, and Figure 14.2-2.1 would be f14\_2\_2\_1.

### Reporting guidelines

- Page Orientation: Landscape.
- Tables and listings: will be created in .rtf.
- Figures: will be generated directly in .rtf.
- Font: Courier New font with minimum of 8-point font size.
- Margins: Left: 3.8 cm, Right: 2 cm, Top: 3 cm, Bottom: 2 cm, on letter paper.
- Columns header will be left aligned for listings.

## 8 Analysis Sets

### All Patients Analysis Set

All Patients Set will include all patients who were enrolled (signed informed consent) regardless of whether they received the study drug or not.

### Full Analysis Set

The full analysis set (FAS) will consist of all patients who received at least one dose of study drug. This analysis set will be used for all efficacy analyses.

For Part B, analyses performed on the FAS will allocate patients' treatment group as randomized.

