## 7 Statistical Considerations

### 7.1 STUDY TREATMENT

The study drug is ulixertinib (BVD-523). The study treatment refers to treatment with ulixertinib (BVD-523). For Part B, the physician's choice treatment will be provided to patients in the comparator arm.

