### Safety Analysis Set

The safety analysis set will consist of all patients who received at least one dose of study drug. This analysis set will be used for all safety analyses.

For Part B, analyses performed on the safety population will allocate patients' treatment group as actually received.

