### 9.8.3 Progression-free Survival (PFS)

The PFS (in months) is defined as the time from the first ulixertinib dose until the first radiographically documented progression of disease or death from any cause, whichever occurs first.

$$PFS = [(Date of first PD/death - Date of first study treatment) + 1] / 30.4375$$

Patients with no documented progression or death will be censored at the last available tumor assessment (last assessment that is CR, PR or SD):

$$PFS = [(Date of last assessment where patient is PD free - Date of first study treatment) + 1] / 30.4375$$

For patients with no post baseline tumor assessment a censored PFS at day 1 will be considered.

$$PFS = (Date of first study treatment - Date of first study treatment) + 1$$

The analysis of PFS will be performed with a Kaplan-Meier method (product-limit estimates) and a summary of associated statistics will be presented including corresponding two-sided 95% CI. The CI for the median will be calculated according to Brookmeyer and Crowley and CI for the survival function estimates at Month 3, 6, 9, 12, and 18 will be derived using the log-log transformation (SAS PROC LIFETEST CONFTYPE=LOGLOG). However, the final choice of timepoints may be updated dependent upon the data.

For Part B, for each histology, PFS curves will be compared between ulixertinib and physician's choice of treatment using Log Rank Test or other appropriate test if the proportional hazards assumption does not hold.

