### 9.8.4 Overall Survival (OS)

The OS (in months) is defined as the time from first treatment to death. Patients who did not die during the study will be censored at the last known alive date.

$$OS = [(Date of death - Date of first study treatment) + 1] / 30.4375$$

For censored patients:

$$OS = [(Last known alive date - Date of first study treatment) + 1] / 30.4375$$

The last known alive date will be determined among study treatment administrations, any visits where at least one assessment has been completed, or any follow-up assessment where the patient has been confirmed to be alive.

OS will be analyzed using the same Kaplan-Meier method used to analyze the DOR.

Part B, OS will be compared between ulixertinib and physician's choice of treatment using a Log Rank Test or other appropriate test if the proportional hazards assumption does not hold.

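### Part B only: the SAP's study-drug wording does not fit the comparator arm, and both documents leave randomised but undosed patients out of the primary comparison

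*SAP*

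**What the plan says.** **Terms and sets in the SAP.** Section 7.1 reads: "The study drug is ulixertinib (BVD-523). The study treatment refers to treatment with ulixertinib (BVD-523". It names physician's choice separately, as what the comparator arm receives. Section 8 then builds two sets on the term. For efficacy: "The full analysis set (FAS) will consist of all patients who received at least one dose of study drug". For safety: "The safety analysis set will consist of all patients who received at least one dose of study drug". In Part B the first set is analysed by randomised group and the second by treatment received.

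**Time origin in the SAP.** Section 9.8.3 defines PFS as the "time from the first ulixertinib dose until the first radiographically documented progression of disease or death from any cause", and its formula subtracts the date of first study treatment. It adds: "For patients with no post baseline tumor assessment a censored PFS at day 1 will be considered". The notes to Table 14.2-1.5.1 and Listing 16.2.6-6 repeat the ulixertinib start. Section 9.8.4 words OS neutrally ("The OS (in months) is defined as the time from first treatment to death"), but its formula is "OS = [(Date of death - Date of first study treatment) + 1] / 30.4375", and the note to Table 14.2-1.6.1 starts OS at the first ulixertinib dose. Section 9.8.3 also says "For Part B, for each histology, PFS curves will be compared between ulixertinib and" physician's choice.

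**Protocol.** Sections 11.4.1 and 11.5.5.2 use the wider terms *study medication* and *trial medication*. The available text defines neither, and Section 8.2.1 uses the first for capsules. The set is still limited to dosed patients, and the clock still starts on the first day of medication. Part B is open-label (11.3). The randomisation code is obtained before Visit 2 (10.3.1.1), where eligibility is reviewed again (10.3.1.2).

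**Status.** SAP Section 4 defers Part B detail to a later version. Section 7.2 records that the study ended during Part A.

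**The concern.** There are two separate matters.

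1. **Wording, SAP only.** If study drug means ulixertinib, a patient given physician's choice has no route into either set and no PFS start date. The SAP cannot apply that definition and also carry out its own comparisons with physician's choice.
2. **Analysis set and clock, both documents.** Correcting the wording leaves a set restricted to patients who started treatment. In an open-label part, a patient can be randomised, learn the arm and leave before dosing. The as-randomised rule does not help, because it only allocates patients who are already in the dosed set.

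What is at stake is whether the Part B primary test compares the groups that randomisation created. If those who leave before dosing differ in prognosis, and the arms differ in how many leave, the test can be biased in either direction.

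**Working it through.** **The plan's own Part B figure (context; not disputed).** Inputs from Protocol 11.2.2: two-sided 5% log-rank test, 80% power, 2:1 allocation, control median PFS 1.7 to 8.5 months, doubled on ulixertinib (hazard ratio 0.5 if PFS is exponential), 24 months' accrual, 18 months' further follow-up, 10% loss to follow-up. Schoenfeld events = (1.960 + 0.842)² / [(2/3)(1/3)(ln 0.5)²] = 7.849 / 0.1068 = 73.5, so 74. The mean event probability is 0.997 at a control median of 1.7 months and 0.762 at 8.5 months, giving N = 75 and 98. Dividing by 0.9 for loss gives 83 and 108. The stated 80 to 100 lies between. The 10% is loss to follow-up; no rate of loss between randomisation and first dose appears.

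**Wording, side by side.**
- Section 7.1 (ulixertinib only), read into the two sets, the PFS start and the OS formula, excludes the comparator arm.
- The as-randomised rule in Section 8, the Part B endpoint in Section 5 (time from trial medication), the comparisons in 9.8.2 to 9.8.4 and the Comparator column in the programming notes all require that arm.
- Read literally, a control enters the set only on crossover, with a PFS clock that starts after the progression that is the event. That cannot be intended.

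**Path of an undosed patient.** Randomisation falls in screening (Day -28 to -1). Eligibility is reviewed again at Visit 2, and discovered ineligibility means withdrawal (Protocol 9.3), so loss before dosing is possible in either arm. Such a patient stays in the SAP's All Patients Set and the disposition table but is in no efficacy set. Even the Part B randomisation listing (16.2.1-4) is on the Full Analysis Set.

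**Widening the set alone is not enough.** The PFS and OS formulas subtract a date that an undosed patient does not have. For PFS, the day-1 rule would then censor anyone without a post-baseline assessment. Death from any cause is a PFS event, but the text does not say which rule governs a patient who dies without a scan. OS has no day-1 rule; it censors at last known alive.

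**Illustration of size (assumed inputs).** Log-rank simulation with no treatment effect: 60 v 30 patients, half of better and half of worse prognosis (hazard ratio 2 or 3 between halves), overall median 1.7, 4 or 8.5 months, follow-up 18 to 42 months, 10% or 20% of the affected arm lost before dosing from one half. The baseline two-sided error is 5.1% to 5.7%. Change in points, dosed-only minus all-randomised, removing an exact count (80,000 replicates; ranges are over the medians):

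| Who is lost | 10%, HR 2 | 10%, HR 3 | 20%, HR 2 | 20%, HR 3 |
|---|---|---|---|---|
| Controls only, better prognosis | 0.56-0.62 | 1.05-1.20 | 2.14-2.23 | 4.20-4.41 |
| Ulixertinib only, better prognosis | 0.08-0.18 | 0.42-0.62 | 1.29-1.37 | 2.88-3.01 |
| Controls only, worse prognosis | 0.08-0.22 | 0.27-0.47 | 0.85-0.88 | 1.92-2.02 |

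The first row favours ulixertinib. The other two run against it: false wins for ulixertinib fall from 2.9%-3.3% to 0.96%-2.34% and 1.22%-2.49%. Losing 20% at random changes the error by -0.1 to +0.1.

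Removing an exact count exaggerates the effect. When each loss is drawn by probability (40,000 replicates), the first row becomes 0.4 to 3.8. At a median of 4 months, 20% lost and HR 3, it falls from 4.2 to 3.4 (Monte Carlo error about 0.2). Read the other two rows for direction. Similar loss in both arms then gives a change near zero.

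**Time origin.** On schedule, randomisation precedes first dose by at most about 28 days (28 / 30.4375 = 0.92 months). The effect of moving the clock was not simulated.

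**The case against.** The strongest reply is that Part B never began. SAP Sections 4 and 7.2 defer its detail to a new version after a protocol amendment, so no planned output is touched. That limits the scope and is accepted. It does not cure the definitions: the Part B sets, endpoints, tests and table notes are written out in the final SAP, and the protocol's stand as written.

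Second, any statistician would read study drug as covering both arms. That is probably right. A reader might infer from Section 7.1 that the whole comparator arm, about 27 to 33 of 80 to 100 patients, would be dropped. The documents do not support that: the as-randomised rule, the comparisons and the Comparator column show that the arm was meant to be analysed. No patient loss is claimed from the wording.

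Third, timing from first dose is stated consistently in the endpoint text of both documents, so it is a design choice. That is fair. The point is that it suits a single-arm part better than a randomised one, and no between-arm difference in dosing delay has been shown.

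Fourth, the simulation inputs are assumptions. The largest figure needs 6 of 30 controls lost, all from a better-prognosis half of about 15 (40% of it), none lost on ulixertinib, and a hazard ratio of 3. This also stands; the figures are illustrative only.

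**Conclusion.** The point holds for any update or reuse of the Part B text and should be fixed there. The study-drug wording is a drafting conflict within the SAP. The dosed-only efficacy set and first-dose clock, in both documents, mean that the Part B primary log-rank test is not strictly a comparison of randomised groups.

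The size is not determinable from the documents. Under the assumptions above, selective loss of better-prognosis controls alone adds about 0.4 to 4 points to two-sided type I error, in favour of ulixertinib. Loss of better-prognosis patients on ulixertinib alone, or of worse-prognosis controls alone, biases against it. Random loss, or similar loss in both arms, leaves the error nearly unchanged.

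A reader might infer that the plan is tilted towards ulixertinib, or that any pre-dose loss inflates the error. Neither follows: the direction depends on who leaves and from which arm, which the documents do not say.

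**What to change.** In the Part B SAP update and the protocol:

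- (a) Define the Part B Full Analysis Set as all randomised patients, analysed as randomised.
- (b) Time PFS and OS from randomisation.
- (c) Define the Part B Safety Set as patients with at least one dose of either assigned treatment, analysed as received.
- (d) Replace the references to first ulixertinib dose and first study treatment in SAP 9.8.3 and 9.8.4 and in the Part B versions of the notes to Tables 14.2-1.5.1 and 14.2-1.6.1 and Listing 16.2.6-6.
- (e) Follow randomised, undosed patients for progression and survival where consent allows, and state that death without a post-baseline scan is a PFS event, so that the day-1 rule does not remove these patients again.

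Leave Part A as it is. The cost is wording in both documents, follow-up of any randomised, undosed patients (Protocol 9.4 and 10.3.7 now tie follow-up to study-drug discontinuation or the start of study therapy), and slight dilution of the estimated effect.

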### Safety Analysis Set

The safety analysis set will consist of all patients who received at least one dose of study drug. This analysis set will be used for all safety analyses.

For Part B, analyses performed on the safety population will allocate patients' treatment group as actually received.

### Per Protocol Analysis Set

The per-protocol analysis set (PP) will consist of all patients of the FAS who completed the study without any important protocol deviations. Prior to any analysis, all patients with important protocol deviations will be reviewed and a decision can be made to include a patient in PP even when there is at least one important protocol deviation. Those cases, if any, will be properly documented in the study report.

### Evaluable Analysis Set

The Evaluable Analysis Set (EAS) will consist of patients from FAS who had the first efficacy evaluation on Study Day 29 $\pm$ 3. Prior to any analysis, all patients data will be reviewed and additional criteria for exclusion from EAS may be added (e.g. occurrence of one or more important protocol deviations). Those cases, if any, will be properly documented in the study report.

For Part A the Full Analysis Set and the Safety Full Analysis Set will be the same. Given that the study was early terminated and an abbreviated CSR focusing mostly on safety data will be prepared, EAS and PP will not be used in any analysis.

## 9 Methods of Analyses and Presentations

### 9.1 PATIENT DISPOSITION

The patient disposition data will be presented by group and overall, for both Part A and Part B on the All Patients Analysis Set. The number and percentage of patients belonging to the following disposition modalities will be presented along with the reason for discontinuation: patients enrolled, patients eligible for inclusion in the study, patients completed/discontinued screening, patients completed/discontinued treatment, patients completed/discontinued study.

The number and percentage of patients in each analysis set will also be presented.

A consort diagram with disposition information will also be provided.

In addition, information on analysis sets, study completion and discontinuation, informed consent and failed inclusion and exclusion criteria will be listed.

For Part B, a listing of randomization will be presented.

### 9.2 PROTOCOL DEVIATIONS AND/OR VIOLATIONS

ICH E3 Q&A R1 defines a protocol deviation as “any change, divergence, or departure from the study design or procedures defined in the protocol”, and important protocol deviations as “a subset of protocol deviations that may significantly impact the completeness, accuracy, and/or reliability of the study data or that may significantly affect a patient's rights, safety, or well-being”. The non-compliance may be either on the part of the patient, the investigator, or the study site staff. The list of potential protocol deviations, including classification (Important/Non-important) for each protocol deviation, will be pre-defined in the Protocol Deviation Criteria Form (PDCF).

Protocol deviations identified during the trial by the Clinical Research Associates (CRAs), Medical Monitors, or Data Managers will be tracked throughout the study using a protocol deviation tracker and classified as Important/Non-important. All protocol deviations will be read into SAS® prior to reporting.

Prior to data lock for the primary and final analyses, a review classification meeting will be held to review protocol deviations and classifications, and to agree on the final analysis sets.

Important protocol deviations will be summarized (frequencies and percentages) by deviation category and summary term for both Part A and Part B on FAS.

A listing of all protocol deviations will be provided for all patients.

### **9.3 DEMOGRAPHIC AND BASELINE CHARACTERISTICS**

The following demographic and baseline characteristics will be summarized using descriptive statistics and presented by group and overall, for both Part A and Part B, on the FAS:

- Age at screening (years), as derived in the eCRF - continuous and categorical using EudraCT categorization (18-64, 65-84,  $\geq$  85)
- Gender
- Childbearing/Reproductive potential
- Ethnicity
- Race
- Height at screening (cm)
- Weight at screening (kg)
- BMI at screening (kg/m^2)
- ECOG performance status at screening
- Smoking history
- Gene (BRAF, MEK1/MAP2K1, MEK2/MAP2K2)
- Codon as reported in the eCRF
- Amino acid change as reported in the eCRF
- NGS Vendors

The following disease history characteristics will be summarized using descriptive statistics and presented by group and overall, for both Part A and Part B, on the FAS:

- Cancer Diagnosis (only reported diagnosis will be displayed, not all categories displayed in the CRF)
- Time since initial diagnosis (in months)
- Disease stage at initial diagnosis (from 1 to 4)
- Disease stage at enrollment (from 1 to 4)
- Method of diagnosis (cytological/histological)
- Prior Cancer Therapies/Regimens (Yes/No)
- Prior BRAF/MEK Inhibitor Therapies (Yes/No)
- Prior Radiation Therapies (Yes/No)

Time since initial diagnosis will be calculated as [(date of first dose of study treatment - date of diagnosis) / 30.4375].

In addition, listings of the above data will be produced for all patients.

A by-patient, detailed listing of smoking history will be also presented.

#### **9.4 MEDICAL HISTORY AND CONCOMITANT DISEASES**

Medical history and concomitant diseases will be coded using MedDRA.

Medical histories are defined as events reported on the Medical History and Disease History eCRF pages, which started before the first study treatment date and were not ongoing at the first study treatment date.

Concomitant diseases are defined as diseases which started before the first study treatment date but were ongoing at the first study treatment date.

The number and percentage of patients with a medical history will be tabulated by group and overall, for both Part A and Part B, by system organ class (SOC) and preferred term (PT) on the Safety Analysis Set. A by-patient listing will be produced.

The number and percentage of patients with a concomitant disease will be tabulated by group and overall, for both Part A and Part B, for each SOC and PT using the FAS. A by-patient listing will be produced.

#### **9.5 PRIOR THERAPIES**

The following summaries will be created by group and overall, for both Part A and Part B, on the FAS:

*Prior radiotherapy:*

- Received at least one prior radiotherapy
- Site of prior radiotherapies (only reported sites will be displayed, not all categories displayed in the eCRF)
- Most recent therapy received before study treatment start: duration of therapy (months) and site

For prior radiotherapy, duration in months will be calculated as  $[(\text{end date of therapy} - \text{start date of therapy}) + 1] / 30.4375$ .

*Prior Anti-Cancer Therapies:*

- Received at least one prior anti-cancer therapy
- Lines of prior anti-cancer therapies
- Most recent therapy received before study treatment start: regimen name, BOR, duration

of therapy (months), time since BOR, time since relapse/progression, and reason for discontinuation.

*Prior BRAF/MEK inhibitor therapies:*

- Received at least one prior BRAF/MEK inhibitor therapy
- Most recent therapy received before study treatment start: treatment name, BOR, duration of BOR, duration of therapy (months), and reason for discontinuation.

For prior anti-cancer therapies, duration in months will be calculated as [(end date of therapy - start date of therapy) + 1] / 30.4375.

Time since BOR (months) will be calculated as [(date of first study treatment - date of BOR)+1] / 30.4375.

Time since relapse/progression (months) will be calculated as [(date of first study treatment - date of Relapse/Progression) + 1] / 30.4375.

For prior BRAF/MEK inhibitor therapies, duration in months will be calculated as [(end date of therapy - start date of therapy) + 1] / 30.4375.

*Prior and Concomitant Medication:*

Medications other than the study treatment will be coded using the WHO Drug Global dictionary. The version of the dictionary will be provided in the corresponding TFLs footnotes.

Medications will be defined as follows:

- Prior Medication: any medications whose end date is before the first study treatment date.
- Concomitant Medication: any medications whose start or end date is either the same or after the first dose of study treatment and up to the end of the on-treatment period.
  - Any medication with a missing medication end date will be assumed to be concomitant medication.
  - Ongoing medications are considered as concomitant medications.

The number and percentage of patients with prior and concomitant medications will be tabulated by group and overall, for both Part A and Part B, by Anatomical Therapeutic Chemical Classification (ATC) and preferred term (PT) on the FAS. A by-patient listing will be produced for prior and concomitant medications as well as for all prior therapies.

*On treatment Radiation, Surgery and Medical Procedures, and Blood Transfusions:*

On treatment Radiation, Surgery and Medical Procedures, and Blood Transfusions will be listed on the FAS.

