8.5 CONCOMITANT THERAPY AND RESCUE MEDICATION

A detailed history of medications, including prior anti-cancer therapies, and procedures will be documented for each patient. Concomitant medications (especially changes in medication, including any anti-cancer therapies) will be documented for each patient at each scheduled visit.

Necessary supportive care such as anti-emetics and anti-diarrheals, etc., will be allowed. Medications that are known to be strong inhibitors or inducers of CYP3A4, CYP2D6, and CYP1A2 are not permitted during the study (for list of non-permitted drugs, see Appendix 1).

If deemed necessary by the treating investigator and reviewed by the medical monitor, palliative radiation therapy for a single site of bone or brain metastasis is allowed provided that it is the only site of disease progression. The radiation field must not affect any of the target lesions designated for disease assessment. Protocol treatment will be held during radiation therapy and will be re-started after any acute toxicities have resolved.

All medications administered from 30 days prior to the commencement of study treatment (Day 1) through the end of the treatment period will be recorded on the eCRF. Any changes of dosages of medication will also be noted.

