**Table 2. Analysis periods**

Phase	Period	Definition
Part A and Part B	PRE-TREATMENT	From informed consent form (ICF) signature to the day before first dose of study treatment.
	ON-TREATMENT	From the day of first dose of study treatment to ≤14 ± 3 days after last dose of study treatment (date of EOT visit), or the earliest date of subsequent anti-cancer drug therapy – 1 day, whichever occurs first.
	FOLLOW-UP	From day ≤14 ± 3 after last dose of study treatment, or the earliest date of subsequent anti-cancer drug therapy, whichever occurs first, to end of study. End of study is date of completion / discontinuation from the study as collected in the CRF or the last recorded assessment in the database if the patient has not completed/discontinued the study at the time of the analysis.

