**PROGRAMMING NOTES:**

- Repeat Table 14.1-3.4
- Present concomitant medications.
- Replace footnote 'Prior medication is defined as...' with the following footnote:  
'Concomitant medication is defined as any medication ongoing at first day of study drug or started after first day of study drug up to the end of the on-treatment period.'

Table 14.1-4.1 - Treatment exposure  
Full Analysis Set

	Group 1 N=XX	Group 2 N=XX	Group 3 N=XX	Group 4 N=XX	Group 5 N=XX	Group 6 N=XX	Overall N=XX
Number of cycles received							
[a] - n (%)							
1	XX (XX.X)						
2	XX (XX.X)						
3	XX (XX.X)						
...							
n	XX						
Mean (SD)	XX.XX (XX.XX)						
Median	XX.XX						
Min; Max	XX.X; XX.X						
Duration of exposure to ulixertinib (months) [b] - n (%)							
< 1 month	XX (XX.X)						
1-2 months	XX (XX.X)						
2-3 months	XX (XX.X)						
...							
n	XX						
Mean (SD)	XX.XX (XX.XX)						
Median	XX.XX						
Min; Max	XX.X; XX.X						

[a] Number of cycles received = Number of cycles where the patient received at least one dose.

[b] Duration of exposure (months) = [(Date of last known treatment dosing with ulixertinib - date of initial dosing with ulixertinib) + 1] / 30.4375.

[c] Actual cumulative dose received (mg) = Sum of [(number of capsules dispensed - number of capsules returned) x 150].

[d] Relative dose intensity = 100 x Actual dose intensity / Planned dose intensity. Actual dose intensity (mg/day) is defined as Actual cumulative dose received (mg) / Duration of exposure (days). Planned dose intensity (mg/day) is defined as Planned cumulative dose (mg) / Duration of exposure (days).

Program: (Program name.sas) (run on: DDMMYYYY HH:MM)

Filename: (Specify file name.rtf)

**Sponsor:** BioMed Valley Discoveries

**Protocol:** BVD-523-ABC

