**Statistical Analysis Plan:**

2.0 / 09-Jun-2023

BioMed Valley Discoveries  
Protocol: BVD-523-ABC ('Delivery' / 'Type') - Part X  
Data extraction date: DDMMYYYY

Page 1 of Y

Listing 16.2.4-8 - Prior and Concomitant Medications  
Full Analysis Set

Group: Group 1

Subject ID	Age / Gender	Reported Term / Preferred Term / ATC Class	Indication	Start Date (Day)	End Date (Day)	Dose (Units) / Frequency	Route	Medication to treat adverse event? / Adverse Event (ID)	Ongoing	Prior / Conc.
xxx-xx	xx/M	Xxxxxxxxxx / xxxxxxxxxxxx / xxxxxx	xxxxxx	DDMMYYYY (xx)	DDMMYYYY (xx)	xxx (xx) / Daily	Oral	Yes / xxxx (x)	Yes	Conc.
xxx-xx	xx/F	xxxxxxxxxxxx / xxxxxxxxxxxx / xxxxxx	xxxxxx	DDMMYYYY (xx)	Ongoing	xxx (xx) / Twice per day	Oral, xxxx	No	No	Prior

Note: M=Male, F=Female, ATC=Anatomical Therapeutic Chemical.

WHOHD-B3 <vx.x>.

Prior medication (Prior): any medications whose end date is before the first study treatment date.

Concomitant medication (Conc.): any medication whose start or end date is either the same or after the first dose of study treatment and up to the end of the on-treatment period.

Program: (Program name.sas) (run on: DDMMYYYY HH:MM)

Filename: (Specify file name.rtf)

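### SAP 9.5 defines concomitant medication by whether a start or end date falls in the on-treatment window, not by overlap, and the table footnote and the protocol define it differently

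*SAP*

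**What the plan says.** Four places define the classification.

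- **SAP 9.5.** A drug is prior if it is among "any medications whose end date is before the first study treatment date". It is concomitant if its "start or end date is either the same or after the first dose of study treatment and up to the end of the on-treatment" period. Two sub-bullets follow: "Any medication with a missing medication end date will be assumed to be concomitant medication", and "Ongoing medications are considered as concomitant medications". Neither sub-bullet mentions the start date.
- **Footnote of Listing 16.2.4-8.** It repeats the main SAP 9.5 rule ("any medication whose start or end date is either the same or after the first dose of study treatment", again up to the end of the on-treatment period) without the sub-bullets.
- **Footnote of Table 14.1-3.5.** Concomitant means "any medication ongoing at first day of study drug or started after first day of study drug", with the end of the on-treatment period as the limit on later starts.
- **Protocol 11.5.4.** It has the same two branches as the table footnote, but no upper limit on later starts.

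SAP Table 2 closes the on-treatment period at the EOT visit "or the earliest date of subsequent anti-cancer drug therapy" minus one day, whichever comes first. Protocol 8.5 says of recording: "Concomitant medications (especially changes in medication, including any anti-cancer therapies) will be documented for each patient at each scheduled visit". The EOT visit is one of those visits. Table 14.1-3.5 and Listing 16.2.4-8 are both marked for inclusion in the final analysis.

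**The concern.** Whether a drug was taken alongside study treatment is a question of overlap between two intervals. SAP 9.5 asks instead whether one of the drug's two dates lies inside the treatment window. A drug that spans the whole window has neither date inside it, so it fails the concomitant rule. Its end date is not before first dose, so it fails the prior rule too.

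The sub-bullets close most of that gap but open another. With no limit on start date, they also take in a drug that began after the on-treatment period had ended. The obvious candidate is a next-line anticancer drug started before the EOT visit, whose start is the very event that closes the window under SAP Table 2.

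At stake is the medication summary in an abbreviated, safety-focused report. A co-medication could be missing from the count. A later anticancer drug could carry a concomitant flag. A table and the listing that supports it could also contradict each other.

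**Working it through.** The plan gives no figure on this point, so the check applies each definition as date logic to the same set of medications.

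**Notation.** F = first-dose date, W = end of the on-treatment period, S and E = the drug's start and end dates.

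- Prior (SAP 9.5): E < F.
- Concomitant, SAP 9.5: F ≤ S ≤ W, or F ≤ E ≤ W, or E missing or ongoing.
- Concomitant, Table 14.1-3.5 footnote: (S ≤ F and the drug has not ended before F), or F < S ≤ W.
- Concomitant, protocol 11.5.4: (S ≤ F and the drug has not ended before F), or S > F.
- Overlap rule proposed here: S ≤ W and (E ≥ F, or ongoing, or E missing).

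**Assumed days, for illustration only.** F = 1, last dose = 90, EOT visit = 90 + 14 = 104, next-line anticancer drug from day 97. By SAP Table 2, W = the earlier of 104 and 97 − 1, which is 96.

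| Medication (S to E) | SAP 9.5 | Table 14.1-3.5 footnote | Protocol 11.5.4 | Overlap rule |
|---|---|---|---|---|
| −20 to −3 | prior | prior | prior | prior |
| −20 to 40 | concomitant | concomitant | concomitant | concomitant |
| −20 to 100 | **no category** | concomitant | concomitant | concomitant |
| −20, ongoing | concomitant (sub-bullet) | concomitant | concomitant | concomitant |
| 50 to 100 | concomitant | concomitant | concomitant | concomitant |
| 97, ongoing | **concomitant (sub-bullet)** | not concomitant | concomitant | post-treatment |
| 97 to 103 | no category | not concomitant | concomitant | post-treatment |

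SAP 9.5 and the table footnote differ on two of the seven, in opposite directions. SAP 9.5 also treats the last two rows differently, although both drugs started on the same day after the window. The only difference between them is whether a stop date was recorded.

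If there is no next-line drug and W = 104, a drug taken from day −20 to day 110 again has no category under SAP 9.5, and is concomitant under the table footnote, the protocol and the overlap rule.

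**Imputed dates.** SAP 7.6 completes a partial end date to the last day of the month or year, or to study discontinuation or completion if earlier. Study discontinuation can fall well after treatment ends, so imputation can push an end date past W. The last row of SAP Table 3 shows the pattern: imputed start 31JAN2017, first dose 27FEB2017, imputed end 31DEC2017. If that patient's on-treatment period closed before 31DEC2017, the drug has no category under SAP 9.5.

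**The case against.** Most of the case on the other side stands.

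- **The first gap is narrow.** Protocol 8.5 records medications only through the end of the treatment period, and the Schedule of Activities has no medication entry after EOT. Without next-line therapy, a drug still in use at EOT is recorded as ongoing and the sub-bullet captures it. The gap needs either a stop between the start of next-line therapy and the EOT visit, or an imputed date.
- **The table shell is sound.** Programmed from its own footnote, Table 14.1-3.5 includes the drug taken throughout and excludes the one begun after the window.
- **The protocol itself counts the later drug.** Under protocol 11.5.4 a drug started after the window is concomitant, so that flag contradicts the table footnote but not the protocol.
- **The data source is not shown.** Listing 16.2.4-8 draws on the Prior and Concomitant Medications page. Listing 16.2.6-7 has its own field for later anticancer treatment. The documents do not say which page holds a next-line drug started before EOT.

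A reader might infer that next-line anticancer drugs will be tabulated as given with ulixertinib, so that the results can no longer be read as single-agent. The documents do not support that. It would require the drug to be on the medications page, to be ongoing or lack an end date, and the table footnote to be ignored. The listing also prints start and end dates, so the sequence would be visible.

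What remains is that a stated derivation rule conflicts with the footnote of the table it feeds, and leaves a drug taken on every treatment day without a category.

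**Conclusion.** The point holds as a definitional error with a narrow reach. As written, SAP 9.5 and the Listing 16.2.4-8 footnote leave a drug that spans the window unclassified when its stop date is known or imputed. The unrestricted sub-bullets can flag a drug begun after the window as concomitant. The Table 14.1-3.5 footnote gives different answers in both situations, and protocol 11.5.4 is a third definition. Two outputs kept for the final analysis can therefore disagree.

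The size is limited to descriptive medication outputs. ORR, DOR, PFS and OS do not use this flag, and TEAEs are defined by the on-treatment period rather than by medication category. No patient count can be given, because the documents do not state how often next-line therapy begins before EOT. A reader might also infer that long-term co-medications, including those restricted by protocol Appendix 1, would commonly disappear. They would not, since a drug that continues is captured as ongoing.

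The conclusion rests on the literal wording of the rules. The next-line example also assumes that such a drug is entered on the medications page.

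**What to change.** Use one overlap rule in SAP 9.5 and in the footnotes of Table 14.1-3.5 and Listing 16.2.4-8: a medication is concomitant if its start date is on or before the end of the on-treatment period and its end date is on or after first dose, or it is ongoing, or its end date is missing. Put the same start-date condition on the two sub-bullets. In Listing 16.2.4-8, label drugs started later as post-treatment. Record in SAP section 11 that this departs from protocol 11.5.4, which sets no upper limit.

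The cost is one sentence and two qualified sub-bullets in SAP 9.5, two footnotes, one listing label and a line in section 11. No new data are needed.
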